2018). This project therefore seeks to: 1) undertake a hydrotherapy intervention in boys and adolescents with DMD and 2) conduct qualitative Patient and Parent interviews to understand the potential barriers and hidden benefits to hydrotherapy not captured in our outcome measures.

Research Objective:

It is hypothesised that undertaking hydrotherapy will result in a beneficial change in the primary outcomes of QoL, bodily pain, and body composition, and secondary outcomes of physical function (e.g. Range of motion strength, and upper limb function), where possible.

The **aim** of this study is to determine whether hydrotherapy can mitigate some of the weight gain, bodily pain, lower QoL and functional impairments associated with progression of DMD in young males.

Potential outcomes include:

- 1) improvements in all outcome measures as a result of undertaking hydrotherapy (increased lean muscle mass, reduced body fat; improved functional measures (e.g. strength), activities of daily living, ROM; improved quality of life, and lowered bodily pain).
- 2) no change in outcome measures following hydrotherapy but a relative slowing of the decline observed during the “control period”.
- 3) outcome measures continue to deteriorate at the same rate as the control period.
- 4) a worsening of outcome measures compared to the control period.

Objectives and Specific Aims:

Outcomes

This project will yield 4 experimental journal articles.

1. The impact of hydrotherapy on body composition and muscle mass in boys with DMD
2. The impact of hydrotherapy on QoL and bodily pain in boys with DMD
3. The impact of hydrotherapy on muscle function and activities of daily living in boys with DMD
4. Practical considerations and barriers to hydrotherapy in young people with DMD, a qualitative review of interviews with parents, carers and those with DMD.

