We are adopting an inclusive approach to participant recruitment, which is possible through the within group design of the control and hydrotherapy interventions. To this end, we aim to recruit 44 male participants aged over 6 years of age, who have previously been diagnosed with DMD from multiple neuromuscular centres in the Northwest Neuromuscular Network (Royal Preston, Manchester, Alder Hey, Oswestry) and from Derian House Children's Hospice (Chorley, UK). Participants will be included if they are able to undertake a single bout of hydrotherapy lasting at least 45 minutes, and are not currently ventilated during the day. An initial assessment will be performed by the clinical physiotherapist associated with the project (See attached *Figure 2-Gant Chart*). Exclusion criteria will include any regular hydrotherapy exercise within the preceding 12 weeks.

There are at present limited data on the effect of hydrotherapy on QoL in DMD from which to base a power analysis, therefore we have carried out our analysis using a previous hydrotherapy intervention in adults with Osteoarthritis (Fransen et al., 2007). It should be noted that their pre intervention QoL scores were similar to those we have collected in DMD participants [DMD = 34.3(5.9), Osteoarthritis = 31.9 (8.5), (Means(SD))].

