Within their 24 sessions of hydrotherapy, Fransen et al (2007) report effect sizes above that of control of 4.0, with no change in their control group. If we make the assumption that within our 12 session intervention we are likely to see half of the improvement in QoL, we shall base our power analysis of an effect size of 2 compared to that of controls. With the following values, within participant *apriori* power calculation performed using G*Power (Version 3.1.7, University of Kiel, Germany) suggests a total group number of n = 8 (α err prob=0.05, Power 0.95). We feel this is too conservative given that we also need to a) account for drop-out of participants and b) fulfil the criteria for parametricity in a clinical condition that has a wide variance (children and adults with DMD ranging from 6-25 yrs are very varied in the presentation of physical function). Therefore, given the aforementioned considerations and as this is a novel intervention in terms of research outcomes and will serve as a primary point of reference for subsequent hydrotherapy studies within DMD, we will recruit 44 participants in total.(See also *table 1*, summarising published hydrotherapy trials in similar medical conditions)

Participants will be recruited through the respective neuromuscular clinic and through Derian House hospice.

Inclusion criteria

- Established diagnosis of Duchenne Muscular Dystrophy (either by genetics or muscle biopsy)
- Between 6 and 25 years of age
- On stable dose of steroids or not on steroids

Exclusion criteria

- Younger than 6 years, older than 25 years
- Recent change in steroid dose, less than 3 months prior
- Undertaking formal hydrotherapy supervised by physiotherapist on a regular basis (weekly or more frequent)

Body composition

Fat mass, body fat percentage and fat free mass will be measured using bioelectrical impedance (BIA). Although more stringent measures of body composition exist such as dual-energy X-ray absorptiometry (DEXA), BIA has been validated in DMD and is accurate enough to measure longitudinal changes in body composition and muscle mass in this population (Mok et al., 2010; Kuru et al., 2019).

Physical function

Established physical function assessments for individuals with neuromuscular conditions will be completed. These will include the North-Star and Performance of the Upper Limb assessment (Mayhew et al., 2013); and an assessment of activities of daily living (Wu et al., 2011).

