The exercises, intensity and specific hydrotherapy session plan will be derived from consultation between the participants, and clinical physiotherapist. Due to the variance within the presentation of the condition and the inclusive age range within the study, we will take what we consider as an externally valid approach to exercise prescription. We will record heart rate during a sample of the participants' hydrotherapy sessions, which will be included as a co-variate for subsequent analysis.

Hydrotherapy will be conducted at Derian House Children's Hospice (Chorley, UK), and may include weight-bearing activities such as standing and gait practice, assisted and resisted limb exercises. Core and trunk work including swimming.

Please find attached

Figure 1-experimental overview

Figure 2-GANTT chart

Figure 3- proposed experimental workflow

Table 1 -current research in hydrotherapy

Data Analysis:

All participants will be assessed using a repeated measures design. Given the broad heterogeneity of DMD participants recruited there is no meaningful benefit of intergroup comparisons between those participants who can complete 30-60 mins of active hydrotherapy, compared to those who can perform arm only, or passive hydrotherapy. Experimentally it is not of interest if one group changes more than another, it is of interest if there is a change within the individuals themselves. We have recently completed a resistance training protocol in adults with MD and adopted a similar approach (Bostock et al., 2019).

Participants will be assessed against previous time points (Pre-CTRL vs Post-CTRL vs Post hydrotherapy) using repeated measures Anova (where outcomes are parametric) or Friedman's (where parametric assumptions are violated). Tests of association will be used to compare relative hydrotherapy intensity with changes from PRE to Post hydrotherapy.

Adverse Events:

All adverse events will be reported to the Chief Investigator and study Sponsor. Depending on the nature of the event the reporting procedures below will be followed. Any questions concerning adverse event reporting will be directed to the Chief Investigator in the first instance.

Adverse Events

If an incident needs acute attention, a member of the research team will follow local emergency procedures.

These will be recorded using the Adverse Event Reporting form, discussed with CI and paediatricians/ physiotherapist of team and escalated to the study Sponsor.

Serious Adverse Events

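### The listed results of slowed decline and same-rate decline compare two 12-week changes, but the named tests compare visits and cannot establish either result

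*Protocol*

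**What the plan says.** The Research Objective section hypothesises a beneficial change in quality of life (QoL), pain and body composition, and then lists four potential outcomes. Two matter here:

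- Item 2: "no change in outcome measures following hydrotherapy but a relative slowing of the decline observed during the" control period.
- Item 3: "outcome measures continue to deteriorate at the same rate as the control period".

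The Data Analysis section assesses participants across pre-control, post-control and post-hydrotherapy visits "using repeated measures Anova (where outcomes are parametric) or Friedman's (where parametric assumptions are violated"). It adds tests of association between hydrotherapy intensity and change. It names no contrast between the two periods and no margin.

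The section on participants and power takes from an osteoarthritis trial that its authors "report effect sizes above that of control of 4.0, with no change in their control group". It halves that figure: "we shall base our power analysis of an effect size of 2 compared to that of controls". With "α err prob=0.05, Power 0.95", the calculation "suggests a total group number of n = 8", and 44 are to be recruited. The section gives SDs of 5.9 (DMD) and 8.5 (osteoarthritis) for QoL scores. It does not say whether the effect of 2 is in scale points or SD units.

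**The concern.** Items 2 and 3 both concern the difference between two changes: post-hydrotherapy minus post-control, compared with post-control minus pre-control. The named tests ask whether the three visits differ. A steady decline through both periods makes the visits differ although hydrotherapy did nothing, so a significant overall test does not answer the question. A non-significant comparison of the last two visits does not show that the outcome was level, or that the rate was unchanged.

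The same non-significant comparison can thus be attached to either of two opposite items. Read as item 2, it claims a slowing that was never tested. Read as item 3, it claims an absence of effect that was never shown. The protocol says the study will inform future activity guidelines and serve as a reference point for later hydrotherapy studies in DMD, so either misreading could carry forward.

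**Working it through.** **Inputs.** From the section on participants and power: SD 5.9, effect 2, alpha 0.05, power 0.95, n = 8 calculated, 44 recruited. Assumed, because the protocol does not give them: two-sided testing, equal SDs, equal correlation r between visits of 0.5 to 0.9, and no dropout.

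**The plan's own figure.** An exact paired t-test with a standardised effect of 2 needs 6 participants two-sided (5 one-sided). An independent-groups test needs 7.6, so 8 per group. Read as 2 points with SD of change 5.9 (r = 0.5), the paired test needs 116; with SD of change 8.5 it needs 237. Only SD units come near n = 8, although halving a QoL improvement from 4.0 to 2 beside raw scores reads like points. Both readings are carried forward.

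**Points reading.** The period contrast is D = (y3 − y2) − (y2 − y1) = y3 − 2·y2 + y1. Its SD is 5.9 × √(6(1 − r)). The 95% half-width is t(0.975, 43) × SD/√44, with t = 2.017. Power for a true 2 points uses the noncentral t.

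| r | SD of D | Half-width | Power for 2 points | Non-significant |
|---|---|---|---|---|
| 0.5 | 10.22 | 3.11 | 25% | 75% |
| 0.7 | 7.92 | 2.41 | 37% | 63% |
| 0.9 | 4.57 | 1.39 | 81% | 19% |

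The farthest limit that a non-significant interval can reach is twice the half-width: 6.21, 4.81 and 2.78 points. Two points can remain inside it at each r. With the 32 participants shown in Table 1, the last column becomes 81%, 72% and 33%.

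A 95% interval can lie wholly within ±2 points only if the half-width is below 2. That needs 6(1 − r) < 4 × 44/(2.017² × 5.9²) = 1.243, so r > 0.79, with an estimate close enough to zero.

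**SD reading.** The half-width is 2.017/√44 = 0.304 SD of the contrast. A non-significant result therefore reaches at most 2 × 0.304 = 0.61 SD. It excludes 2 SD but does not show sameness.

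**Error in the other direction (item 2).** Take a steady decline of 1 point in each period, no treatment effect, SD 5.9 and n = 44. In simulation, a significant control-period decline followed by a non-significant hydrotherapy-period change occurred in about 19%, 26% and 27% of trials at r = 0.5, 0.7 and 0.9. That pattern looks like slowed decline, yet the rates are identical. The 1-point decline is an illustration, not a protocol figure.

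**The case against.** - **The list is not a set of reporting rules.** A reader might infer that a non-significant result will be reported as no effect. The protocol does not say so. It presents the items as potential outcomes, and the list need not be exhaustive. This stands, so the point is about what the stated analysis could support.
- **Item 2 is not a null finding.** A reader might infer that both items are no-effect conclusions. Item 2 counts holding steady as slowed decline, in line with the aim of mitigating decline. This stands, and it means the error there runs towards false benefit.
- **Item 3 also requires continued deterioration.** A flat result over all three visits would not fit it. True, but decline in both periods still does not show equal rates.
- **The planned benefit may be excluded.** A reader might infer that any null result leaves the full planned effect possible. That can be so on the points reading; on the SD reading it is false.
- **The contrast is not named in the plan, and its size depends on r.** Both are correct: 19% to 75% is a wide range and applies to QoL only. The missing contrast is part of the problem. It is the quadratic contrast of a three-visit ANOVA, so obtaining it is easy.
- **Interpretation rules often sit in an SAP.** That is fair for margins and interval reporting, and their absence alone would be no finding. But the protocol itself fixes tests that do not match the results it lists.

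**Conclusion.** The point holds in a limited form. Difference tests between visits neither estimate the difference between the two 12-week changes nor can establish an equal rate. A non-significant post-control to post-hydrotherapy comparison could be taken as item 2 or item 3 and supports neither.

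How much this matters for QoL depends on the unit of the planning effect. In points, the trial would often be unable to separate a 2-point benefit from none unless between-visit correlation is high. In SDs of the change, the planned effect would be excluded and the remaining uncertainty is about 0.6 SD. The points figures rest on SD 5.9, 44 completers and equal correlations. The protocol gives no SD or planning effect for pain or body composition, so no size can be given for them.

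**What to change.** 1. In Data Analysis, report for each primary outcome the estimate and 95% confidence interval of hydrotherapy change minus control change. Use a bootstrap or rank-based interval where Friedman's test would have been used. Base items 1 to 4 on that interval.
2. In Research Objective, add *inconclusive* as a possible result. Use *same rate* only where the interval excludes a difference stated in advance as meaningful for that outcome.
3. For QoL, set that difference no wider than the planning effect and state its unit. The other primary outcomes need their own stated difference, because the protocol has no planning effect for them.

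No new visits or data are needed. The cost is one interval per outcome and agreement on a meaningful difference for each. The downside is that some outcomes, including QoL on the points reading, will be labelled inconclusive.

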As the first hydrotherapy study within DMD, the overarching outcome will be to determine whether it is efficacious and beneficial to complete a longitudinal hydrotherapy intervention in young males with DMD, which will inform future guidelines on activity within this population. To this end we will conduct qualitative interviews and work alongside the members of the Northwest Neuromuscular network, and the Neuromuscular Centre (Winsford, UK) who regularly undertake hydrotherapy to engage with service users with DMD to provide guidelines for physical activity based on our previous work on sedentary behaviour (Jacques et al., 2018) and the findings of this proposed project.

Qualitative interviews

Face-to-face interviews will be conducted with 20 participants from the study. This will include a mixture of those with DMD, and their parents, to understand what barriers are faced when undertaking hydrotherapy, what about the hydrotherapy intervention was suitable, and whether there are benefits to hydrotherapy not captured in our outcome measures (Bagley et al., 2016). The interviews will be approached from an interpretivist perspective to make sense of the lived

experiences of those involved in the hydrotherapy (Schwartz-Shea and Yanow, 2013), consistent with the expertise within our research team. In addition to a scientific publication, these qualitative findings will inform the development of future guidelines on hydrotherapy and allow us to optimise participant benefit through relevant research.

Rationale and Significance of Study:

Protocol design justification

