While natural history studies indicate an overall negative trend in the abilities of patients with DMD, there is great variability in age and speed of deterioration (Muntoni et al., 2019). As such it is difficult to find matched controls for a short randomised intervention study. Instead, due to the progressive nature of DMD and the inherent variance within a mixed age, and ability population (e.g. upper limb & respiratory function, genetic variation etc.(Ricotti et al., 2019)), the participants will act as their own controls. This single-arm, non-crossover design where the participant acts as his own control, although not as robust as randomized control exercise trials, is advocated for longitudinal interventions in populations such as the present one (Hecksteden et al., 2018). Indeed, this self-controlled approach offers some of the benefits of prospective controlled trials, allows for multiple treatments within the same participants, and eliminates some of the covariates of group comparisons which are inherent in dual arm training studies (Vohra et al., 2015). Specifically with treatments such as hydrotherapy, the process of randomisation leads to patient and parent disengagement due to not getting to undertake a treatment (Hind et al., 2017). This self-controlled study avoids the downsides of randomisation for the participants and is consistent with previous exercise training studies both in non-clinical (Narici et al., 1989), and in our own training studies in muscular dystrophy (Bostock et al., 2019).

Research Design

The **aim** of this project is to undertake 12-weeks of hydrotherapy in boys and adolescents with DMD, and monitor the impact on body composition, bodily pain, QoL and physical function. The project is broken down into 3 key stages:

Pre-experimental stage: during this stage we will secure ethical approval, and recruit participants. This stage will last ~6 months due to the length of time it takes to secure NHS ethical approval.

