Experimental stage: the participants will complete the experimental protocol described below in detail. Briefly, participants will complete TWO 12-week periods. The first will be an observation (control) period to use as a reference point for the second period, which will involve 12-weeks of hydrotherapy. *Figure 1* attached describes the testing sessions; these will be completed at 3 time points, the first before the control period, the second after the control period, and the third after the hydrotherapy period. The experimental stage will last 28-months due to the staggered recruitment and testing of participants.

Post experimental stage: this stage will involve the analysis of data and production of academic papers for submission within international journals. This stage will be scheduled for 4-months but will continue until the data has been published. Although the cost of a dissemination event is not formally included within this bid; as researchers and clinicians we regularly update physiotherapists, carers, clinicians and those with DMD through dissemination events. We plan to present our findings at events hosted through the

Northwest Neuromuscular Network, The Neuromuscular Centre outreach and dissemination days, and through the hospice website.

Experimental stage protocol

Participants will complete two 12-week periods, including an initial control period (CTRL), where they will undertake their habitual physical activity behaviour. This will be followed by 12-weeks of hydrotherapy, where participants will complete up to 60 mins of hydrotherapy once a week. During these CTRL and hydrotherapy periods, diet and physical activity will be monitored to identify any lifestyle covariates that could contribute to their body composition and physical and mental wellbeing. Pre and Post CTRL, and Post hydrotherapy, participant outcome measures will be re-assessed.

Consent: consent will be obtained from patients 16 years and older or parents / guardians of children younger than 16 years of age, either face to face or via a pre-arranged video link with a member of the research team who is signed off the delegation log as being able to take consent.

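### The Protocol promises a verdict on whether hydrotherapy is efficacious, but a single-arm, fixed-order comparison with self- or proxy-reported QoL and pain cannot separate hydrotherapy from contact, expectation or period effects

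*Protocol*

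**What the plan says.** **Conclusion intended.** Under Objectives and Specific Aims (Outcomes), the Protocol says "the overarching outcome will be to determine whether it is efficacious and beneficial to complete a longitudinal hydrotherapy intervention in young males with DMD". The same sentence gives the use to be made of that finding: "which will inform future guidelines on activity within this population". Under Research Objective the hypothesis is causal: "It is hypothesised that undertaking hydrotherapy will result in a beneficial change in the primary outcomes of QoL, bodily pain, and body composition". The aim that follows asks whether hydrotherapy can lessen weight gain, pain, reduced QoL and functional decline.

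**Design.** Protocol design justification describes it thus: "This single-arm, non-crossover design where the participant acts as his own control, although not as robust as randomized control exercise trials, is advocated". Experimental stage protocol sets "an initial control period (CTRL), where they will undertake their habitual physical activity behaviour", followed by 12 weeks with one session a week. The Intervention section puts each session at 30 to 60 minutes, with content agreed between the participant and the clinical physiotherapist. Assessments fall before the control period, after it, and after hydrotherapy. Diet and physical activity are monitored in both periods.

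**Primary outcomes.** QoL is measured by questionnaires, including a proxy form. Pain is measured by a pain map and body composition by bioelectrical impedance. No blinding is described.

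**Analysis.** Data Analysis compares the three time points by repeated-measures ANOVA or Friedman's test, and relates hydrotherapy intensity to change.

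**The concern.** The control period lets each participant serve as his own reference for the course of the disease. It does not supply a reference for the other things that begin when hydrotherapy begins. In the second period a participant attends a weekly appointment, works with a therapist and knows that he is being treated. He is also 12 weeks older and has been tested once more. QoL and pain are the primary outcomes most open to these influences, because the reporter knows the period.

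If the stated aim stands, a favourable QoL or pain difference could be read as demonstrated efficacy and enter guidance on that footing. The choice of test does not affect this. It concerns what the comparison can identify, so a statistical analysis plan could not repair it while the Protocol's aim remains as worded.

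**Working it through.** The Protocol gives no figure on this point, so none is reproduced or disputed.

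**1. What the comparison contains.** Let D1 be a participant's change over the control period and D2 his change over the hydrotherapy period.

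- D1 = T1 + R1
- D2 = T2 + R2 + H + C + E

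T is time-related change (disease course, season), R is repeat-testing effect, H is hydrotherapy, C is session contact and E is expectation. Subtracting:

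D2 − D1 = H + C + E + (T2 − T1) + (R2 − R1)

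There is one observable contrast and several unknowns. The control period removes time and testing effects only if they are equal in both periods. It removes neither C nor E. With everyone in the same order, no analysis of these data separates the terms. The planned association with intensity does not help, because intensity is agreed for each participant rather than allocated and will tend to follow ability.

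**2. Which primary outcomes are exposed.**

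| Primary outcome | Measurement | Exposure to unblinded reporting |
|---|---|---|
| QoL | Self- and proxy-report questionnaires | Yes |
| Bodily pain | Pain map | Yes |
| Body composition | Bioelectrical impedance | Much less, though contact could alter diet or activity |

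That is two of three. Among the other measures, grip strength and spirometry are read from instruments but depend on effort, so they are not free of expectation.

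**3. Difference in scheduled session contact.** 12 sessions × 0.5 h = 6 h; 12 sessions × 1.0 h = 12 h; control period 0 h of study hydrotherapy sessions. The zero covers those sessions only. Assessments and monitoring occur in both periods, and the consent section refers to physiotherapy that the child receives.

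**4. Would a larger sample help?** This is an illustration under an assumption. Suppose H = 0 and non-hydrotherapy influences shift a reported outcome by b standard deviations of the paired difference. The documents give no b; 0.1 to 0.5 is assumed. As a simplification of the planned analysis, take a two-sided paired t-test at 0.05. The test statistic is then noncentral t with n − 1 degrees of freedom and noncentrality b√n. For b = 0.3 and n = 44, the noncentrality is 0.3 × 6.633 = 1.99 against a critical value of 2.02, so the chance of significance is about one half.

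| b (assumed) | n = 44 (planned) | n = 20 (figure in the Background) |
|---|---|---|
| 0.1 | 9.9% | 7.1% |
| 0.2 | 25.4% | 13.6% |
| 0.3 | 49.4% | 24.7% |
| 0.4 | 73.7% | 39.7% |
| 0.5 | 90.0% | 56.5% |

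The table shows direction only: if such a shift exists, recruiting more participants makes it more likely to reach significance.

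**The case against.** The strongest reply is that the design is disclosed and argued. The Protocol calls it "although not as robust as randomized control exercise trials" and gives reasons: variable deterioration, lack of matched controls, and disengagement under randomisation. It describes the control period as a reference for the second, individualises the sessions, and never claims to isolate water or exercise from therapist contact. Participants cannot be blinded to being in a pool, so unblinded QoL and pain would affect any hydrotherapy trial against usual care. Guidelines are also to draw on interviews, network members and earlier work.

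Much of this stands. The design is defensible, and neither randomisation nor blinding is being asked for. Staggered recruitment should also spread season across participants, although nothing guarantees balance. What does not stand is the step from a general concession to an unqualified efficacy aim. The justification does not mention contact, expectation or period effects, and the concession does not limit the conclusion.

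Some stronger readings are tempting but unsupported:

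- "improvements in all outcome measures as a result of undertaking hydrotherapy" might be read as attributing results in advance. It is one of four listed scenarios, which also include unchanged decline and worsening.
- The remark on disengagement might be read as evidence that expectation biases reported QoL and pain. It concerns families who did not get the treatment under randomisation. Here everyone is offered it, and the remark says nothing about reporting.
- One might conclude that a QoL or pain change is at least an effect of the whole programme. A fixed-order single arm does not establish that either, because time, season and repeat testing remain.

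**Conclusion.** The concern holds as a mismatch between the stated aim and the design. The study can estimate whether change differs between the two periods. It cannot determine that hydrotherapy is efficacious, and for QoL and pain the gap is widest. The change should be made, but the mismatch does not invalidate the study.

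The conclusion rests on the fixed order, the absence of any matched contact described for the control period, and the reported nature of two of three primary outcomes. Lack of blinding is inferred from the design and from the Protocol's silence; it is not stated in words.

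A reader might take the 6 to 12 hours against 0, or the significance rates above, as the size of the problem. They are not. The first counts contact, the second follows from an assumed shift, and the documents show neither that a bias exists nor how large it would be.

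**What to change.** 1. In Research Objective and in Objectives and Specific Aims, replace the efficacy wording with: *to estimate the change during a supervised weekly hydrotherapy programme relative to the preceding control period*.
2. State in advance that differences in QoL and pain will not be reported, or carried into guideline statements, as established efficacy of hydrotherapy, because contact, expectation and period effects cannot be excluded. Do not substitute a statement that they are an effect of the whole programme.
3. Report QoL and pain beside body composition by bioimpedance, noting that it is less exposed to reporting bias. Where grip and spirometry are shown, note that they depend on effort.

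The cost is wording and a more modest headline claim. No new data, visits or participants are needed.

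### The prior-hydrotherapy exclusion is worded in two different ways, so a site screening from the list alone could admit a participant who has only just stopped, which would affect comparisons against the control-period change

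*Protocol*

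**What the plan says.** Two places in the protocol set the exclusion.

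- **Participants and power calculation (narrative):** "Exclusion criteria will include any regular hydrotherapy exercise within the preceding 12 weeks". This covers any regular hydrotherapy and looks back 12 weeks. It has no supervision condition and no stated frequency.
- **Exclusion criteria (list):** "Undertaking formal hydrotherapy supervised by physiotherapist on a regular basis (weekly or more frequent". This is in the present tense, covers only formal supervised sessions, sets a weekly threshold and has no look-back. The steroid item in the same list does carry a look-back: "Recent change in steroid dose, less than 3 months prior".

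The design makes the control period the yardstick. Under Protocol design justification, "participants will act as their own controls". Under Research Design, "The first will be an observation (control) period to use as a reference point for the second period". Among the potential outcomes listed under Research Objective is "no change in outcome measures following hydrotherapy but a relative slowing of the decline observed during the" control period. During that period participants continue as usual, "where they will undertake their habitual physical activity behaviour".

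**The concern.** The two wordings give different answers for a participant who attended weekly supervised hydrotherapy until shortly before his Pre-CTRL assessment. The narrative excludes him; the list, read alone, does not. Recruitment runs through four named neuromuscular centres and a hospice, so sites could screen differently depending on which text they work from.

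The difference matters because there is no parallel control group. If such a participant loses ground during the control period because his hydrotherapy ended, that loss enters the reference change as though it were disease progression. The hydrotherapy period could then appear to slow a decline that was partly the result of stopping the same kind of treatment.

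Prior exposure is plausible but not shown. The Background says hydrotherapy is recommended in boys with DMD, and recruitment includes the hospice where the study sessions are held.

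**Working it through.** There is no stated figure to reproduce, so the check has two parts.

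**1. The two texts applied to the same cases**

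| Candidate | Narrative rule | List alone |
|---|---|---|
| Weekly supervised sessions, ongoing | Excluded | Excluded |
| Weekly supervised sessions, stopped 2 weeks before Pre-CTRL | Excluded | Not excluded |
| Regular supervised sessions, less than weekly | Excluded, if that counts as regular | Not excluded |
| Regular unsupervised pool exercise | Depends on what counts as hydrotherapy exercise | Not excluded |

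The second row is the clear difference. It assumes only that the 12 weeks run back from entry or Pre-CTRL, which is the natural reading of an eligibility rule. The last two rows depend on definitions that the protocol does not give. No other section reconciles the two texts or says which governs screening.

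**2. Which comparisons are exposed**

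Let A, B and C be the group means at Pre-CTRL, Post-CTRL and Post hydrotherapy, on a scale where higher is better. Suppose a share f of participants are recent stoppers, and each loses an extra d during the control period. Assume that the loss is complete by Post-CTRL and that the change during the hydrotherapy period is not altered. B and C are then each lower by f × d than they would otherwise be, and A is unchanged.

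- Control-period change, B − A: shifted by −f × d.
- Hydrotherapy-period change, C − B: shifted by −f × d − (−f × d) = 0.
- Hydrotherapy change judged against control change, (C − B) − (B − A): shifted by 0 − (−f × d) = +f × d.

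The apparent slowing of decline is therefore overstated by f × d, while the Post-CTRL to Post-hydrotherapy comparison taken alone is not moved. If the loss was already complete before Pre-CTRL, all three means shift equally and every comparison above is unbiased. If the loss continues past Post-CTRL, C − B is shifted downwards, against hydrotherapy.

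The protocol gives neither f nor d, so no numerical size follows.

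**The case against.** The strongest reply is that the texts do not truly conflict. The narrative says the exclusion criteria will include its rule, which is not exhaustive wording, and a person who meets either exclusion is excluded. The same narrative paragraph also holds entry conditions that are absent from the lists: tolerating a single session of at least 45 minutes, and not being ventilated during the day. The list is therefore not a complete set, and its silence on the 12 weeks does not show that the look-back was dropped. This stands. A reader might infer a flat contradiction in which the look-back has been abandoned, and the protocol does not support that. What survives is that the cumulative reading is nowhere stated, and the list is headed as the exclusion criteria and could be used for screening on its own.

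A second reply is that Data Analysis specifies repeated-measures ANOVA or Friedman's test across three time points, not a difference of changes. This also stands, and it limits the point to interpretation against the control-period change. That interpretation is nonetheless the protocol's own, in Research Objective and Research Design.

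A third reply is that lifestyle is tracked: "diet and physical activity will be monitored to identify any lifestyle covariates". This helps only in part. Accelerometers are planned for up to 7 days in the first week of each period, which cannot show hydrotherapy before Pre-CTRL.

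**Conclusion.** The concern holds as a drafting inconsistency with a possible consequence for the control-period reference. The prior-hydrotherapy exclusion is worded differently in two places, and a site using the list alone would admit a recent stopper whom the narrative excludes. Eligibility is a protocol matter, so this is not detail to be left to a statistical analysis plan.

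The size is unknown. A reader might infer that the treatment effect is overstated by some sizeable fraction. The protocol does not support any such figure, because both the share of recent stoppers and their loss would have to be invented. A reader might also infer that the hydrotherapy-period change itself is biased. Under the assumptions set out above it is not, and the exposure is confined to comparisons against the control-period change. With other timings of the loss the bias could vanish or change direction, so its net direction is not established.

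The inconsistency should be corrected because doing so is cheap and the design has no other control.

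**What to change.** Reconcile the narrative under Participants and power calculation with the Exclusion criteria list, so that there is one prior-hydrotherapy exclusion used at all recruiting sites. Either carry the 12-week look-back into the list, timed to the Pre-CTRL assessment, or justify its removal.

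Two additions are optional: saying whether unsupervised pool exercise such as swimming counts, and keeping a brief log of hydrotherapy taken outside the study during both periods.

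The cost is protocol wording and an updated screening form. The downside is that a few candidates may have to wait or be excluded, which works slightly against the inclusive recruitment aim and the target of 44.
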